11.8 Appendix 8. Response Evaluation Criteria in Solid Tumors Version 1.1 (RECIST v1.1)

Quick Reference

Definitions

- Measurable Lesions
 - Measurable Tumor Lesions Non-nodal lesions with clear borders that can be accurately measured in at least 1 dimension with longest diameter ≥ 10 mm in computed tomography/magnetic resonance imaging (CT/MRI) scan with slice thickness no greater than 5 mm. When slice thickness is greater than 5 mm, the minimum size of measurable lesion should be twice the slice thickness.
 - Nodal Lesions Lymph nodes are to be considered pathologically enlarged and measurable, a lymph node must be ≥ 15 mm in short axis when assessed by CT/MRI (scan slice thickness recommended to be no greater than 5 mm). At baseline and in follow-up, only the short axis will be measured and followed.
 - Nodal size is normally reported as 2 dimensions in the axial plane. The smaller of these measures is the short axis (perpendicular to the longest axis).
 - Irradiated Lesions Tumor lesions situated in a previously irradiated area, or in an area subjected to other loco-regional therapy, are not measurable unless there has been demonstrated progression in the lesion prior to enrollment.
- Non-measurable Lesions
 - All other lesions, including small lesions (longest diameter < 10 mm or pathological lymph nodes with ≥ 10 mm but to < 15 mm short axis with CT scan slice thickness no greater than 5 mm) are considered non-measurable and characterized as non-target lesions.
 - Other examples of non-measurable lesions include:
 - Lesions with prior local treatment: tumor lesions situated in a previously irradiated area, or an area subject to other loco-regional therapy, should not be considered measurable unless there has been demonstrated progression in the lesion.
 - Biopsied lesions
 - Categorially, clusters of small lesions, bone lesions, inflammatory breast disease, and leptomeningeal disease are non-measurable.

Methods of Measurement

- Measurement of Lesions The longest diameter of selected lesions should be measured in the plane in which the images were acquired (axial plane). All measurements should be taken and recorded in metric notation. All baseline evaluations should be performed as closely as possible to the beginning of treatment and not more than 4 weeks before study Day 1.
- Methods of Assessment The same method of assessment and the same technique should be used to characterize each identified and reported lesion throughout the trial.
- CT/ MRI Contrast-enhanced CT or MRI should be used to assess all lesions. Optimal visualization and measurement of metastasis in solid tumors requires

consistent administration (dose and rate) of intravenous (IV) contrast as well as timing of scanning. Computed tomography and MRI should be performed with \leq 5 mm thick contiguous slices.

Baseline documentation of "Target" and "Non-target" lesions

- Target Lesions All measurable lesions up to a maximum of 2 lesions per organ and 5 lesions in total, representative of all involved organs should be identified as target lesions and recorded and measured at baseline.
 - Target lesions should be selected on the basis of their size (lesions with the longest diameter) and suitability for accurate repeated measurements.
 - Pathologic lymph nodes (with short axis ≥ 15 mm) may be identified as target lesions. All other pathological nodes (those with short axis ≥ 10 mm but < 15 mm) should be considered non-target lesions.
 - A sum of the diameters (longest for non-nodal lesions, short axis for nodal lesions) for all target lesions will be calculated and reported as the baseline sum of diameters. The baseline sum of diameters will be used as reference by which to characterize objective tumor response.
- Non-Target Lesions All other lesions (or sites of disease) including pathological lymph nodes should be identified as non-target lesions and should also be recorded at baseline. Measurements of these lesions are not required, and these lesions should be followed as "present", "absent", or "unequivocal progression" throughout the study. In addition, it is possible to record multiple non-target lesions involving the same organ as a single item on the CRF (eg, "multiple enlarged pelvic lymph nodes" or "multiple liver metastases").

Response Criteria

Evaluation of Target Lesions

Complete Response (CR)	Disappearance of all target lesions. Any pathological lymph nodes (whether target or non-target) must have reduction in short axis to < 10 mm.
Partial Response (PR)	At least a 30% decrease in the sum of the diameters of target lesions, taking as reference the baseline sum of diameters.
Progressive Disease (PD)	At least a relative 20% increase and an absolute increase of 5 mm in the sum of the diameters of target lesions, taking as reference the smallest sum on study, or the appearance of 1 or more new lesions.
Stable Disease (SD)	Neither sufficient shrinkage to qualify for PR nor sufficient increase to qualify for PD, taking as reference the smallest sum of diameters since the treatment started.

Evaluation of Non-target Lesions

Complete Response (CR):	Disappearance of all non-target lesions and normalization of tumor marker level. All lymph nodes must be non-pathological in size (< 10 mm short axis).
Incomplete Response/Stable Disease (SD)	Persistence of one or more non-target lesions(s) and/or maintenance of I' level above the normal limits.
Progressive Disease (PD)	Unequivocal progression of existing non-target lesions and/or appearance of one or more new lesions ^a .

^a To achieve "unequivocal progression" on the basis of the non-target disease, there must be an overall level of substantial worsening in non-target disease such that, even in presence of SD or PR in target disease, the overall tumor burden has increased sufficiently to merit discontinuation of therapy. A modest "increase" in the size of 1 or more non-target lesions is usually not sufficient to qualify for unequivocal progression status.

Evaluation of Overall Response

The best overall response is the best response recorded from the start of the study treatment until the end of treatment or disease progression/recurrence (taking as reference for progressive disease [PD] the smallest measurements recorded since the treatment started).

In general, the subject's best response assignment will depend on the findings of both target and non-target disease and will also take into consideration the appearance of new lesions.

Target Lesions	Non-target Lesions	New Lesions	Overall Response
CR	CR	No	CR
CR	Non-CR/non-PD	No	PR
CR	Not evaluated	No	PR
PR	Non-PD or not all evaluated	No	PR
SD	Non-PD or not all evaluated	No	SD
Not all evaluated	Non-PD	No	NE
PD	Any	Yes or No	PD
Any	PD	Yes or No	PD

Time Point response:	Subjects with	Target (+ Non-targe	t) Disease
	Oubjects with	Turger (.	± non-targo	U DISCUSC

CR = complete response; PD = progressive disease; PR = partial response; NE = not evaluable; SD = stable disease.

Time Point Response: Subjects with Non-target Disease Only

Non-target Lesions	New Lesions	Overall Response
CR	No	CR
Non-CR/non-PD	No	Non-CR/non-PD ^a
Not all evaluated	No	NE
Unequivocal PD	Yes or No	PD
Any	Yes	PD

CR = complete response; PD = progressive disease.

^a "Non-CR/non-PD" is preferred over "SD" for non-target disease since SD is increasingly used as endpoint for assessment of efficacy in some trials, so to assign this category when no lesions can be measured is not advised.

Overall Response: Confirmation of Complete Response (CR) and Partial Response (PR) required

Overall Response First Time Point	Overall Response Second Time Point	Best Overall Response
CR	CR	CR
CR	PR	SD, PD or PRª
CR	SD	SD provided minimum criteria for SD duration met, otherwise, PD
CR	PD	SD provided minimum criteria for SD duration met, otherwise, PD
CR	NE	SD provided minimum criteria for SD duration met, otherwise, NE
PR	CR	PR
PR	PR	PR
PR	SD	SD
PR	PD	SD provided minimum criteria for SD duration met, otherwise, PD
PR	NE	SD provided minimum criteria for SD duration met, otherwise, NE
NE	NE	NE

CR = complete response; PD = progressive disease; PR = partial response; NE = not evaluable; SD = stable disease.

^a If a CR is truly met at first time point, then any disease at a subsequent time point, even disease meeting PR criteria relative to baseline, makes the disease PD at that point (since disease must have reappeared after CR). Best response would depend on whether minimum duration for SD was met. However, sometimes "CR" may be claimed when subsequent scans suggest small lesions were likely still present and in fact that subject had PR, not CR at the first time point. Under these circumstances, the original CR should be changed to PR and the best response is PR.

Special Notes on Response Assessment

- Nodal lesions Lymph nodes identified as target lesions should always have the actual short axis measurement recorded, even if the nodes regress to below 10 mm on study. In order to qualify for complete response (CR), each node must achieve a short axis < 10 mm, NOT total disappearance. Nodal target lesion short axis measurements are added together with target lesion' longest diameter measurements to create the sum of target lesion diameters for a particular assessment (timepoint).
- Target lesions that become "too small to measure" While on study, all lesions (nodal and non-nodal) recorded at baseline should have their measurements recorded at each subsequent evaluation. If a lesion becomes less than 5 mm, the accuracy of the measurement becomes reduced. Therefore, lesions less than 5 mm are considered as being "too small to measure" and are not measured. With this designation, they are assigned a default measurement of 5mm. No lesion measurement less than 5 mm should be recorded, unless a lesion totally disappears and "0" can be recorded for the measurement.
- New lesions The term "new lesion" always refers to the presence of a new finding that is definitely tumor. New findings that only may be tumor, but may be benign (infection, inflammation, etc.) are not selected as new lesions, until that time when the review is certain they represent tumor.
 - If a new lesion is equivocal, for example because of its small size, continued therapy and follow-up evaluation will clarify if it represents truly new disease. If repeat scans confirm there is definitely a new lesion, then progression should be declared using the date of the initial scan.
 - A lesion identified on a follow-up study in an anatomical location that was not scanned at baseline is considered a new lesion and will indicate disease progression, regardless of any response that may be seen in target or non-target lesions present from baseline.
- Subjects with a global deterioration of health status requiring discontinuation of treatment without objective evidence of disease progression at that time should be classified as having "symptomatic deterioration." Every effort should be made to document the objective progression with an additional imaging assessment even after discontinuation of treatment.
- In some circumstances it may be difficult to distinguish residual disease from scar or normal tissue. When the evaluation of CR depends on this determination, it is recommended that the residual lesion be further investigated by fluorodeoxyglucose-positron emission tomography (FDG-PET) or PET/CT, or possibly fine needle aspirate/biopsy, to confirm the CR status.

Confirmation Measurement / Duration of Response

- **Response Confirmation** In non-randomized trials where response is the primary endpoint, confirmation of PR and CR at least 4 weeks after the initial assessment is required to ensure responses identified are not the result of measurement error.
- **Duration of overall response** The duration of overall response is measured from the time measurement criteria are first met for CR/PR (whichever is first recorded) until the first date the recurrent or PD is objectively documented.
- **Duration of Stable Disease** SD is measured from the start of the treatment until the criteria for disease progression are met, taking as reference the smallest measurements recorded since the treatment started.

11.9 Appendix 9. Eastern Cooperative Oncology Group Performance Status

Eastern Cooperative Oncology Group (ECOG) Performance Status

0 – Fully active, able to carry on all pre-disease performance without restriction

1 – Restricted in physically strenuous activity, but ambulatory and able to carry out work of a light or sedentary nature (eg, light housework, office work)

2 – Ambulatory and capable of all selfcare, but unable to carry out any work activities. Up and about more than 50% of waking hours

3 – Capable of only limited selfcare, confined to bed or chair more than 50% of waking hours

- 4 Completely disabled. Cannot carry out any selfcare. Totally confined to bed or chair
- 5 Dead

11.10 Appendix 10. Examples of Excluded Treatments

Examples of sensitive clinical substrates for CYP3A-mediated metabolism

alfentanil, avanafil, budesonide, buspirone, conivaptan, darifenacin, darunavir, dasatinib, dronedarone, ebastine, eletriptan, eplerenone, everolimus, felodipine, ibrutinib, indinavir, lomitapide, lovastatin, lurasidone, maraviroc, midazolam, naloxegol, nisoldipine, quetiapine, saquinavir, sildenafil, simvastatin, sirolimus, tacrolimus, ticagrelor, tipranavir, tolvaptan, triazolam, vardenafil

Examples of strong clinical inhibitors for CYP3A-mediated metabolisms

boceprevir, clarithromycin, cobicistat, conivaptan, danoprevir and ritonavir, diltiazem, elvitegravir and ritonavir, grapefruit juice, idelalisib, indinavir and ritonavir, itraconazole, ketoconazole, lopinavir and ritonavir, nefazodone, nelfinavir, paritaprevir and ritonavir and (ombitasvir and/or dasabuvir), posaconazole, ritonavir, saquinavir and ritonavir, telaprevir, tipranavir and ritonavir, troleandomycin, voriconazole

Examples of strong clinical inducers for CYP3A-mediated metabolisms

carbamazepine, enzalutamide, mitotane, phenytoin, rifampin, St. John's wort

Source: https://www.fda.gov/drugs/drug-interactions-labeling/drug-development-and-drug-interactions-tablesubstrates-inhibitors-and-inducers

Amendment 4

Protocol Title: A Phase 1, Open-label Study Evaluating the Safety, Tolerability, Pharmacokinetics, and Efficacy of AMG 510 in Subjects of Chinese Descent With Advanced/Metastatic Solid Tumors With *KRAS p.G12C* Mutation (CodeBreaK 105)

Amgen Protocol Number AMG 510 20190147

Amendment Date: 05 January 2022

Rationale:

This protocol has been amended mainly to:

- Update dosage modification guidelines for hematologic and non-hematologic toxicities (Section 6.2.3.1, Table 6-3) and dosing instructions for AMG 510 (Section 6.1.1, Table 6-1) as the Amgen investigational product in the study.
- Update key safety information to be monitored in the clinical study, newly added information pertaining to thyroid abnormalities, and interstitial lung disease/pneumonitis (Section 2.3).
- Clarify definition of AMG 510 overdose and instructions for the physician/investigator to manage such event (Section 6.6).
- Add information regarding the treatments that must be avoided prior to enrollment and during the study period (Sections 6.1.7 and 6.7.2) and instructions on how to administer such medications (concomitant medications) in case they are considered a medical necessity (ie, antacid therapy).
- Update instructions for reporting serious adverse events observed by the investigator or reported by the subject during the study and after end of study (Sections 1.3 and 8.2.4) as well as language related to definitions and procedures for recording, evaluating, follow-up and reporting safety events (Section 11.4).

- Clarify that standard of care treatment (eg, procedures, laboratory studies) can be used during the screening process if they were conducted within the 28-day screening window prior to cycle 1 day 1 (Sections 1.1, 5, 8.1.1).
- Clarify nature of laboratory assessments in the schedule of activities (ie, lipid panel) and inform that local urinalysis and coagulation assessments are at the discretion of the investigator (Section 1.3, 11.2).
- Add background information regarding AMG 510 as a new approved treatment for adult patients with *KRAS pG12C*-mutated locally advanced or metastatic non-small cell lung cancer (Section 2.2.1).
- Clarify that individuals who experience a screen failure may be rescreened up to 2 times (Section 5.3).
- Update study assessments and procedures to describe alternative methods to continue safety assessments and study medication in patients unable to visit the study sites (Section 8) and to describe requirement for completion of physical measurements (Sections 1.3 and 8.2.1.5).
- Add language pertaining to Coronavirus disease 2019 (COVID-19) related benefit/risk assessment (Section 2.3).
- Add strategies to increase data quality assurance including implementation of the remote Source Data Review and Verification and read-only access for the clinical monitor to the electronic medical record system (Section 11.3).
- Provide general clarifications about the use of investigational medical devices in this study (Section 6.1.3) and about product complaints (Section 6.1.6).
- Multiple changes for clarification, administrative, typographical, and formatting were made throughout the protocol.

Amendment 3

Protocol Title: A Phase 1, Open-label Study Evaluating the Safety, Tolerability, Pharmacokinetics, and Efficacy of AMG 510 in Subjects of Chinese Descent With Advanced/Metastatic Solid Tumors With *KRAS p.G12C* Mutation (CodeBreaK 105)

Amgen Protocol Number AMG 510 20190147

Amendment Date: 16 December 2020

Rationale:

This protocol is being amended to:

- To add additional subjects at a dose level considered safe and tolerable by the dose level review team (DLRT) to collect additional pharmacokinetic (PK), safety, and preliminary efficacy data.
- To clarify allowable time windows for visits and study-required assessments.
- To add additional concomitant medication use information regarding gastric acid controllers based on developing pharmacokinetic data.
- Updates to statistical sections to align with the addition of more subjects to the study.
- Corrections and clarifications to the analyte Table 11-1.

Amendment 2

Protocol Title: A Phase 1, Open-label Study Evaluating the Safety, Tolerability, Pharmacokinetics, and Efficacy of AMG 510 in Subjects of Chinese Descent With Advanced/Metastatic Solid Tumors With KRAS p.G12C Mutation (CodeBreaK 105)

Amgen Protocol Number AMG 510 20190147

Amendment Date: 18 September 2020

Rationale:

This amendment is being updated to:

- Remove the timing requirement for predose safety lab assessments
- Changes to eligibility to have received an anti-PD(L)1 and/or platinum as well as received 2 prior systemic therapies rather than 3
- Clarification of a second DLRM for the second cohort
- Remove thyroid panel assessment at cycle 1 day 1
- Added key safety information (increases in AST and ALT)
- Other administrative changes (typographical, formatting)

Amendment 1.0

Protocol Title: A Phase 1, Open-label Study Evaluating the Safety, Tolerability, Pharmacokinetics, and Efficacy of AMG 510 in Subjects of Chinese Descent With Advanced/Metastatic Solid Tumors with *KRAS p.G12C* Mutation (CodeBreak 105)

Amgen Protocol Number: AMG 510 20190147

Amendment Date: 04 February 2020

Rationale:

The below AMG 510 program-wide changes were incorporated into the study:

- Thyroid function, cholesterol, and triglyceride tests were added to the Schedule of Activities in this study to make it consistent with Study 20170543 that was amended to address regulatory agency feedback (US Food & Drug Administration)
- Removed food restriction for AMG 510 at cycle 2 day 2 and beyond (after intensive pharmacokinetics assessments) as the studies evaluating the effect of food (high fat meal) on pharmacokinetic characteristics of AMG 510 demonstrated that high-fat meal does not appear to result in clinically meaningful alteration of AMG 510 exposure
- Removed reference to "30 tablets/bottle" to allow flexibility in AMG 510 supply
- Updated language for AMG 510 dose modification to allow additional dose reductions of AMG 510 in the case of indicated toxicities
- Added AMG 510 Hepatotoxicity Guidelines for management and monitoring of subjects with increased AST, ALT, or ALP while on trial
- Revised the Contraceptive Guidance and Collection of Pregnancy and Lactation Information based on data from recently completed nonclinical studies (absence of genotoxic risk for AMG 510 based on recently completed GLP-compliant in vitro bacterial mutagenicity Ames assay and in vivo genotoxicity study including the erythrocyte micronucleus test and the alkaline comet assay).
- Modified hepatotoxicity stopping rules (Appendix 7) to align with guidelines for the management of AMG 510 hepatotoxicity

Other Changes:

- Added CodeBreak 105 study name
- Removed exploratory objective/endpoint to identify metabolites of AMG 510 in plasma and urine
- Modified header rows in Schedule of Activities to clarify that assessments on cycle 2 day 8, cycles 3,5;4,6; QC and Q2C will be completed prior to dosing
- Clarified timepoints for electrocardiogram and vital signs assessments in Schedule of Assessments footnote e

- Changed language to allow MRI brain scans to be performed in all subjects at screening, and in subjects with brain metastases or history of brain metastases at other indicated timepoints
- Added language to update AMG 510 nonclinical toxicology information with 3-month dog and rat results.
- Added language to clarify the definition of predose and timepoint window for predose laboratory assessments
- Added language to clarify the minimum time interval for determination of stable disease
- Modified table of analyte listings in Appendix 2 to include new laboratory tests
- Corrected the number of target lesions for RECIST v1.1 in Appendix 8
- Added language to clarify that an assessment of PR and CR must be confirmed ≥ 4 weeks after the initial assessment
- Added a new appendix to present examples of excluded treatments
- Administrative and editorial updates

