- 219 Male subjects with a pregnant partner who are unwilling to practice abstinence or use a condom during treatment and for an additional 7 days after the last dose of AMG 510
- 220 Male subjects unwilling to abstain from donating sperm during treatment and for an additional 7 days after the last dose of AMG 510
- 221 Subject has known sensitivity to any of the products to be administered during dosing
- 222 Subject likely to not be available to complete all protocol-required study visits or procedures, and/or to comply with all required study procedures to the best of the subject and investigator's knowledge
- 223 Subject has any kind of disorder that, in the opinion of the investigator, may compromise the ability of the subject to give written informed consent and/or to comply with all required study procedures
- 224 History or evidence of any other clinically significant disorder, condition or disease (with the exception of those outlined above) that, in the opinion of the investigator or Amgen physician would pose a risk to subject safety or interfere with the study evaluation, procedures or completion
- 225 Use of known CYP3A4 and P-gp-sensitive substrates (with a narrow therapeutic window), within 14 days or 5 half-lives of the drug or its major active metabolite, whichever is longer, prior to study day 1 that was not reviewed and approved by the Principal Investigator and the Amgen Medical Monitor
- 227 Use of strong inducers of CYP3A4 (including herbal supplements such as St. John's wort) within 14 days or 5 half-lives (whichever is longer) prior to study day 1 that was not reviewed and approved by the Principal Investigator and the Amgen Medical Monitor.
- History of other malignancy within the past 2 years, with the following exceptions:
 - Malignancy treated with curative intent and with no known active disease present for ≥ 2 years before enrollment and felt to be at low risk for recurrence by the treating physician.

- Adequately treated non-melanoma skin cancer or lentigo maligna without evidence of disease.
- Adequately treated cervical carcinoma in situ without evidence of disease.
- Adequately treated breast ductal carcinoma in situ without evidence of disease.
- Prostatic intraepithelial neoplasia without evidence of prostate cancer.
- Adequately treated urothelial papillary non-invasive carcinoma or carcinoma in situ without evidence of disease.
- 229 Previous treatment with a KRAS^{G12C} inhibitor
- 230 Leptomeningeal disease

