6.1.7 Excluded Treatments, Medical Devices, and/or Procedures During Study Period

The following medications and supplements to be avoided for 14 days prior to enrollment and during the study period unless reviewed and approved by the Principal Investigator and the Amgen Medical Monitor:

- Known strong inducers of CYP3A4 including herbal supplements, such as St. John's wort
- Known CYP3A4 and P-gp-sensitive substrates with a narrow therapeutic window unless approved by Amgen medical monitor
- Proton pump inhibitors (PPI) and H2-receptor antagonists unless approved by Amgen medical monitor

If a subject needs palliative radiotherapy for pain control during the course of the study, all study drugs should be discontinued, and the investigator or designee should notify the sponsor as soon as possible. A subject may be allowed to resume study drug after discussion between the Amgen Medical Monitor and the investigator to determine the appropriateness of treatment resumption.

Subjects must not schedule any major elective surgeries during the treatment period, and for at least 28 days after the last administration of AMG 510. Minor elective surgery may be allowed after discussion with the Amgen Medical Monitor. If a subject undergoes any unexpected surgery during the course of the study, AMG 510 must be discontinued, and the investigator or designee should notify the sponsor as soon as possible. A subject may be allowed to resume AMG 510 only if both the investigator and Amgen Medical Monitor agree to restart study therapy.

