6.7.2 Concomitant Treatment

Throughout the study, investigators may prescribe any concomitant medications or treatments deemed necessary to provide adequate supportive care except for those listed in Section 6.1.7.

Concomitant administration of AMG 510 with **PPI (eg, Omeprazole) or** H2-receptor antagonists (eg, famotidine) decreased AMG 510 concentrations, which may reduce AMG 510 efficacy. Avoid use of PPI or H2-receptor antagonists with AMG 510. If antacid therapy is considered medically necessary, administer AMG 510 4 hours before or 10 hours after administration of a local antacid.

Breast cancer resistance protein substrates should be used with caution when co-administered with AMG 510 which may increase the circulating concentration of BCRP substrates.

Amgen will review all concomitant medications with the investigators prior to dosing with AMG 510 to ensure patient safety.

All concomitant therapies (including all prescription, over-the-counter medications) are to be collected from enrollment through the end of the SFU period and will be recorded on the eCRF.

For concomitant therapies, collect therapy name, indication, dose, unit, frequency, route, start date and stop date.

7. Discontinuation Criteria

Subjects have the right to withdraw from investigational product and/or other protocol-required therapies, protocol procedures, or the study as a whole at any time and for any reason without prejudice to their future medical care by the physician or at the institution.

The investigator and/or sponsor can decide to withdraw a subject(s) from investigational product, device, and/or other protocol-required therapies, protocol procedures, or the study as a whole at any time prior to study completion for the reasons listed in Sections 7.1, 7.2.1, and 7.2.2.

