6.2 Pharmacokinetic Analyses Set(s)

The PK Analysis Set will contain all subjects who have received at least dose of AMG 510 and have at least 1 PK sample collected. These subjects will be evaluated for PK analysis unless the number of data points required for analysis is not enough, or significant protocol deviations have affected the data, or if key dosing or sampling information is missing.

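### Appendix 10 presents strong CYP3A inhibitors as excluded, Sections 5.2 and 6.1.7 do not name them and Section 6.7.2 permits them by default; the PK analysis has no flag for profiles taken on such drugs or on approved acid reducers

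*Protocol*

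**What the plan says.** The appendix is titled "11.10 Appendix 10. Examples of Excluded Treatments". It gives examples of three classes: sensitive CYP3A substrates, strong CYP3A inhibitors ("Examples of strong clinical inhibitors for CYP3A-mediated metabolisms") and strong CYP3A inducers.

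The operative sections are narrower. In Protocol Section 5.2, criterion 225 covers CYP3A4 and P-gp sensitive substrates with a narrow therapeutic window, and criterion 227 covers strong CYP3A4 inducers. Section 6.1.7 lists "Known strong inducers of CYP3A4 including herbal supplements, such as St. John's wort", the same narrow-window substrates, and proton pump inhibitors (PPI) and H2-receptor antagonists. All of these may be used if approved. Neither section names CYP3A inhibitors.

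Protocol Section 6.7.2 lets investigators prescribe "any concomitant medications or treatments deemed necessary to provide adequate supportive care except for those listed in Section 6.1.7". It also says that the sponsor will go through concomitant medications with investigators before dosing, and that PPI and H2-receptor antagonists lowered AMG 510 concentrations.

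On the analysis side, SAP Section 6.2 takes subjects with at least one dose and one PK sample and then says "These subjects will be evaluated for PK analysis unless" there are too few data points, a significant protocol deviation affected the data, or key dosing or sampling information is missing. SAP Section 4.1 plans no covariates. SAP Section 9.7.1 plans non-compartmental Cmax, tmax and AUC, with no mention of interacting drugs.

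**The concern.** Two sites could treat the same patient differently and each point to the protocol. One relying on Section 6.7.2 may prescribe a strong CYP3A inhibitor; one relying on Appendix 10 must treat it as excluded. In the text available, no section of the protocol body refers to Appendix 10, so nothing says which governs.

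PK characterisation is one of two primary objectives, and Section 2.1 says that the data will be set against the global first-in-human study to look for ethnicity-associated differences. Each cohort has 6 to 12 subjects, so a single unusual profile carries weight in a mean. The protocol controls food through cycle 2 day 1 and records food status on PK days (Section 8.2.6). Leaving co-medication unmarked sits oddly with that care.

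**Working it through.** No figure in the plan bears on this point, so the check is a comparison of the passages followed by an illustration of size.

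**Passages side by side**

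| Class | Appendix 10 | Section 5.2 | Section 6.1.7 | Result under Section 6.7.2 |
|---|---|---|---|---|
| Strong CYP3A inducers | listed | criterion 227, unless approved | listed, unless approved | not permitted without approval |
| Sensitive CYP3A substrates | listed, no narrow-window limit | criterion 225, narrow window only, unless approved | narrow window only, unless approved | other sensitive substrates permitted |
| Strong CYP3A inhibitors | listed | not named | not named | permitted if needed for supportive care |
| PPI and H2-receptor antagonists | not listed | not named | listed, unless approved | to be avoided; approval possible |

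The inhibitor row is the contradiction. The substrate row is a smaller mismatch, because Appendix 10 omits the narrow-window limit.

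**What the PK set does with such profiles**

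1. Inhibitor use leads to removal only as a significant deviation. It is a deviation if Appendix 10 governs and is not one if Sections 6.1.7 and 6.7.2 govern.
2. Approved use of a drug in Section 6.1.7 follows the protocol, so the deviation rule does not reach it. For PPI and H2-receptor antagonists the protocol itself reports an effect on AMG 510 concentrations, yet such a profile stays in the summary unmarked.
3. SAP Section 9.3 lets deviation categories be updated until database lock, so the status of inhibitor use could be settled after concentrations are known.

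**Size, by assumption**

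Inputs: n = 6 or 12 per cohort (Protocol Section 9.4.1.2). The planned statistics are means, medians, standard deviations and ranges (SAP Section 9.1). Geometric means are not named there and are shown for reference. The documents give no effect of CYP3A inhibitors on AMG 510, so the AUC multiplier f in one subject is assumed to lie between 1.0 (no effect) and 3.

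- Arithmetic mean, if the affected subject's AUC would otherwise equal the cohort mean: ratio = 1 + (f - 1)/n.
- Geometric mean: ratio = f^(1/n).

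| f | Arithmetic, n = 12 | Arithmetic, n = 6 | Geometric, n = 12 | Geometric, n = 6 |
|---|---|---|---|---|
| 1.0 | 1.00 | 1.00 | 1.00 | 1.00 |
| 1.5 | 1 + 0.5/12 = 1.04 | 1 + 0.5/6 = 1.08 | 1.03 | 1.07 |
| 2 | 1 + 1/12 = 1.08 | 1 + 1/6 = 1.17 | 1.06 | 1.12 |
| 3 | 1 + 2/12 = 1.17 | 1 + 2/6 = 1.33 | 1.10 | 1.20 |

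The median is better protected. With 12 subjects it lies midway between the 6th and 7th ordered values. Raising one subject's value, however far, can move it at most to midway between the original 7th and 8th.

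For PPI and H2-receptor antagonists the shift would be downward. The documents give no size, so none is calculated.

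**The case against.** Several points on the other side stand.

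- Sections 5.2 and 6.1.7 are silent on inhibitors; they do not permit them. Permission comes only through Section 6.7.2 and only for supportive care. The sponsor's review before dosing, and the general exclusion in criterion 224, could keep users out of the cycle 1 profiles. Neither names inhibitors or sets a rule, so they reduce the problem without settling it.
- Appendix 10 gives examples. Its substrate and inducer lists can be read as illustrating the classes in criteria 225 and 227. Only the inhibitor list has no counterpart.
- The PK set does have a deviation rule, and unapproved use of a drug in Section 6.1.7 could fall under it. The gap is confined to inhibitors and to approved use.
- The fuller sampling series fall on cycle 1 days 1 and 8, with a shorter one on cycle 2 day 1, so mainly early use matters.

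A reader might also infer that the missing number 226 marks a deleted inhibitor criterion. The documents do not say what 226 covered, so the gap proves nothing.

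A reader might further infer that inhibitor use would distort exposure and pass for an ethnic difference. The documents do not establish this. Protocol Section 2.2.2.2 describes oxidative and conjugative metabolism in nonclinical species without naming an enzyme, and calls AMG 510 a P-gp substrate in vitro. The restriction on strong inducers makes an effect plausible, no more. A false ethnic signal would also require inhibitor use to differ between this study and the global one, whose co-medication rules are not given.

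**Conclusion.** The inconsistency is in the current text and a site cannot follow both readings. Its effect on the PK results is possible but unquantified. Under the assumed 1.0- to 3-fold change in one subject's AUC, the arithmetic mean rises 0-17% (1 of 12) or 0-33% (1 of 6) and the geometric mean 0-10% or 0-20%; the median would usually move much less. The lower end is zero because no inhibitor effect on AMG 510 is stated.

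The part that needs no assumption about inhibitors concerns acid reducers. The protocol says that they lowered AMG 510 concentrations, allows them with approval, and the SAP has no means of marking the affected profiles. That alone justifies a flag in a primary PK summary of 6 to 12 subjects.

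**What to change.** Protocol: reconcile Appendix 10 with Sections 5.2, 6.1.7 and 6.7.2, covering both the inhibitor list and the missing narrow-window limit on substrates, and have the body refer to the appendix. Which list stands is for the sponsor to decide.

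SAP Section 9.7.1: flag each PK profile taken while the subject was on a drug that could alter AMG 510 exposure, namely a strong CYP3A inducer, a PPI or H2-receptor antagonist, or a strong CYP3A inhibitor. Show Cmax and AUC with and without flagged profiles. Do not flag CYP3A substrates: Section 2.2.2.2 describes AMG 510 acting on CYP3A, which bears on the substrate's exposure and not on that of AMG 510.

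Cost: protocol wording and one extra summary based on small numbers. Names, doses and start and stop dates of concomitant therapies are already collected (Section 6.7.2), as are those for the 28 days before enrollment (Section 6.7.1). Grapefruit juice, which is in the inhibitor list, may not be recorded as a medication and could escape the flag.
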